3. TEMPLATE VERSION HISTORY (FILLED IN BY QA)

OP Document Number	Version	Change Description	Change Date
T-10118	1.0	Initial release	26-Jun-2023

4. DOCUMENT VERSION HISTORY

OP Document Number	Version	Change Description	Change Date
VER-DOC-527	1.0	Initial release	30-Jun-2023
VER-DOC-527	2.0	Protocol Synopsis and Section 5.8: reworded IEC1 (removed future tense)	01-Aug-2023

**LUMINIZE_CLINICAL_PROTOCOL**Document ID: VER-DOC-527
Controlled Document: VER-SIGN-3084TEMPLATE:
ONEPROJECTS/SIGN-267

Version: 4.0

Project: VERAFEYE (VER)
Date: 22-Nov-2024 14:16:10
Page: 4 / 51

OP Document Number	Version	Change Description	Change Date
		
Section 5.4.3.2: Figure 4: replaced with an updated figure
 
Section 5.10.3.4:
 
• 12-lead ECG to be obtained at the end of the procedure• Fluoroscopy time will be measured for the entire procedure; fluoroscopy dose will be measured 
Throughout document: administrative corrections were made (section numbering was corrected).
 
Section 5.15.2: section on source documents was added.
	
VER-DOC-527	3.0	
Section 5.4.2:
 
Deleted size of catheter
 
Picture of the VERAFEYE Imaging catheter removed
 
Section 5.4.3.2: clarified that Figure 3 is an example of the room setup during a procedure
 
Section 5.10.3.3:
 
VERAFEYE imaging data will only be collected from the right atrium.
 
Clarified that standard of care imaging = standard of care echocardiography imaging (intracardiac echocardiography (ICE), transesophageal echocardiography (TEE))
 
Section 5.10.3.4: VERAFEYE imaging time replaced with time VERAFEYE imaging catheter was in the body
 
Section 5.13.1: Reportable events were updated
	18-Dec-2023
VER-DOC-527	4.0	
Protocol Synopsis: number of subjects updated to 40, Georgia removed as potential country
 
Table 1: VERAFEYE System components description restructured to improve clarity
 
Section 5.4: Device description updated to be aligned with IFU
 
Section 5.7:
 
• Added that up to 4 operators per site will be allowed to perform	22-Nov-2024

**LUMINIZE_CLINICAL PROTOCOL**Document ID: VER-DOC-527
Controlled Document: VER-SIGN-3084TEMPLATE:
ONEPROJECTS/SIGN-267

Version: 4.0

Project: VERAFEYE (VER)
Date: 22-Nov-2024 14:16:10
Page: 5 / 51

OP Document Number	Version	Change Description	Change Date
		
study procedures, unless written approval from LUMA Vision was obtained
 
• Added that enrolment in this study is competitive• Added that subject procedures will follow a sequential pattern (one site after the other)• Number of subjects updated to 40 and rationale explained 
Section 5.9.1 and 5.9.2: Number of subjects updated to 40, Georgia removed as potential country
 
Section 5.10.3.1: Added that up to 4 operators per site will be allowed to perform study procedures, unless written approval from LUMA Vision was obtained.
	

5.1. CONTACT INFORMATION

Position	Details
Sponsor	LUMA Vision Ltd. [name]
Coordinating Principal Investigator	[name]. [name] [name], FESC, FEHRA Mater Private Network Heart & Vascular Centre [name]

**LUMINIZE_CLINICAL PROTOCOL**Document ID: VER-DOC-527
Controlled Document: VER-SIGN-3084TEMPLATE:
ONEPROJECTS/SIGN-267

Version: 4.0

Project: VERAFYE (VER)
Date: 22-Nov-2024 14:16:10
Page: 7 / 51

	Ireland Email: [contact]
Clinical Manager	[name] [contact] [contact]
Clinical Research Engineer	[name] [contact] [contact]

5.2. PROTOCOL SYNOPSIS**Study title:** LUMINIZE: Luma Vision's feasibility study on the VERAFEYE system**Study Objective:** The objective of the study is to collect data on the usability and integration of the VERAFEYE System in

- standard of care catheter-based ablation treatments for Typical Atrial Flutter (AFL) or Atrial Fibrillation (AF)
- standard of care left atrial appendage (LAA) closure procedures
- standard of care atrial septal defect (ASD) closure procedures

Results from this study will be used to guide development and refinement the VERAFEYE System.

Indication for Use: The VERAFEYE System is indicated for intracardiac and intraluminal ultrasound visualization of cardiac and great vessel anatomy and physiology as well as visualization of other devices in the heart and great vessels of patients.**Clinical Investigation Device:** VERAFEYE System, comprising of

- **VIC** - VERAFEYE Imaging Catheter
- **CIU** - Catheter Interface Unit
- **SC** – System Console

Control Device: NA**Study Design:** The LUMINIZE study is a prospective, non-randomized, single-arm feasibility study.

**LUMINIZE_CLINICAL PROTOCOL**Document ID: VER-DOC-527
Controlled Document: VER-SIGN-3084TEMPLATE:
ONEPROJECTS/SIGN-267

Version: 4.0

Project: VERAFYE (VER)
Date: 22-Nov-2024 14:16:10
Page: 8 / 51

Planned Number of Subjects: Enrolment will be considered as complete when 40 subjects have completed the ablation, or LAA/ASD closure procedure with the VERAFYE System as imaging system.

Planned Number of Sites/Countries: Up to 2 sites in Ireland may participate in this study.

Study Endpoints: This is a feasibility study and no formal endpoints or hypothesis testing are planned in the study. The study is not designed to collect data for product approval and as such does not have a safety or efficacy endpoint.

Inclusion Criteria:

- IC1: Subject is 18 to 80 years of age at the time of consent
- IC2: Subject is scheduled to undergo a standard of care*, de-novo catheter-ablation procedure to treat typical AFL or AF

or

- left atrial appendage (LAA) closure procedure

or

- atrial septal defect (ASD) closure procedure

**according to current international and local guidelines and currently approved indications*

- IC3: Subject is able to understand and willing to provide written informed consent
- IC4: Subject is able and willing to complete all study assessments

Exclusion Criteria:

- EC1: Any of the following within 6 months prior to enrolment:
 - Cardiac surgery including coronary artery bypass grafting, ventriculotomy, atriotomy
 - Thromboembolic event (stroke), transient ischemic attack (TIA) or neurological disturbances
 - Myocardial infarction
 - Any surgical or percutaneous cardiac procedure including coronary intervention and cardiac ablation
 - Dilated or hypertrophic cardiomyopathy
- EC2: Any planned surgical or endovascular intervention within 30 days before or after the ablation, or LAA/ASD closure procedure.
- EC3: Any of the following cardiac conditions:
 - New York Heart Association (NYHA) class IV
 - Left ventricular ejection fraction (LVEF) < 30%
 - Implanted with a cardiac rhythm management device (pacemaker, CRT, ICD, loop recorder)

**LUMINIZE_CLINICAL PROTOCOL**Document ID: VER-DOC-527
Controlled Document: VER-SIGN-3084TEMPLATE:
ONEPROJECTS/SIGN-267

Version: 4.0

Project: VERAFFEYE (VER)
Date: 22-Nov-2024 14:16:10
Page: 9 / 51

- Presence of intramural thrombus, tumor, or other abnormality that precludes vascular access, catheter introduction, or manipulation
- Active coronary ischemia, significant valvular heart disease, or hemodynamically significant congenital cardiac abnormality
- EC4: Body mass index (BMI) > 40 kg/m²
- EC5: Body weight < 50kg
- EC6: Pregnant women or women who plan to become pregnant during the course of their participation in the study (women should either be of non-childbearing potential at the time of enrolment (as documented in the medical file) or have a negative pregnancy test within the previous 7 days prior to the ablation, or LAA/ASD closure procedure)
- EC7: Life expectancy less than 12 months
- EC8: Subjects who are currently enrolled in another study

Imaging Exclusion Criteria:

- IEC1: Subjects with a thrombus or pericardial effusion detected in the LA/LAA during standard of care imaging.

Subject Follow-Up: A study subject's participation will be considered complete when all protocol required visits have been completed. For subjects who underwent the ablation, or LAA/ASD closure procedure, subject participation in the study is concluded at 7 days follow-up.

Study Duration and Participant Duration: Enrolment in the study is expected to be completed in approximately 6 months. The follow-up for each participant is expected to be approximately 7 days, therefore the total study duration is expected to last approximately 7 months.

Statistical Methods: There are no statistical methods to be employed in this feasibility study. Analysis of study data will use descriptive statistical methods.

Procedure/Assessment	Baseline Visit	Procedure Visit	Post-Procedure Visit	7- Day Follow-Up (office visit/phone call)
	≤ 60 days prior to Day 0	Day 0	Day 0- Day 2	Day 7 ± 2 days

**LUMINIZE_CLINICAL_PROTOCOL**Document ID: VER-DOC-527
Controlled Document: VER-SIGN-3084TEMPLATE:
ONEPROJECTS/SIGN-267

Version: 4.0

Project: VERAFYE (VER)
Date: 22-Nov-2024 14:16:10
Page: 10 / 51

Procedure/Assessment	Baseline Visit	Procedure Visit	Post-Procedure Visit	7- Day Follow-Up (office visit/phone call)
Informed Consent Form and Process	X			
Eligibility Criteria	X			
Demographics including age and gender	X			
Medical history	X			
Physical Assessment	X	X	X	
Cardiac imaging*	X		(X)	(X)
Medication regimen	X	X	X	X
Procedural data collection		X		
Investigational Data Collection		X		
Device Performance		X		
Protocol Deviations	X	X	X	X
Adverse Events	X	X	X	X
Device Deficiencies		X		

*: per hospital standard of care

(): optional, collect only if performed per hospital's standard of care

5.3. BACKGROUND

With an increasing number of interventional procedures performed for structural heart disease and cardiac arrhythmias each year, echocardiographic guidance is necessary for safe and efficient results⁽¹⁾.

**LUMINIZE_CLINICAL PROTOCOL**Document ID: VER-DOC-527
Controlled Document: VER-SIGN-3084TEMPLATE:
ONEPROJECTS/SIGN-267

Version: 4.0

Project: VERAFYE (VER)
Date: 22-Nov-2024 14:16:10
Page: 11 / 51

²⁾. Both transthoracic (TTE) and transesophageal echocardiography (TEE) are available echo options but have their limitations. Intracardiac echocardiography (ICE) provides advantages over TTE and TEE by providing imaging from within the heart, providing shorter image distances and higher resolution. Additionally, it is known that ICE has the benefit of avoiding general anesthesia, reducing procedure time and reducing x-ray exposure in comparison to other techniques. Studies have also reported that ICE may reduce periprocedural complications as compared with TEE. At the same time, the efficacy of procedures guided by ICE appear to be comparable to procedures guided by other imaging techniques. Importantly, echocardiography features as a key part of standard practice as recommended in all clinical practice guidelines referred to in this review; four of the guidelines name ICE specifically as an acceptable or standard imaging option⁽³⁻⁶⁾. The growing body of evidence finding ICE to have comparable efficacy, and perhaps superior safety and added benefits relative to TEE, gives evidence that ICE is a critical part of the state of the art for intraprocedural imaging in Atrial Fibrillation (AF), Atrial Flutter (AFL), Left Atrial Appendage Closure (LAAC) and Atrial Septal Defect Closure (ASDC).

Although transcatheter procedures for ablating tissues or closing cardiac defects are well established in standard practice, success rates and durability of those treatments have not reached satisfactory levels. AF after ablation, for example, commonly recurs in 25-50% of procedures or more⁽⁷⁻¹¹⁾. This leaves patients at higher risk for stroke and in need of additional procedures which incur additional risk. While clinical guidelines make recommendations to mitigate these risks, and studies are assessing procedural improvements and treatment modifications such as adding additional ablation lines or substrates to improve the acute and long-term outcomes, there remains a need for additional device advancements. Factors such as catheter-tissue contact⁽¹²⁾ and precision of tag placement⁽¹³⁾ in PVI have been shown to relate to durability of the ablation and ultimately to better long-term outcomes. Although contact-force catheters and other imaging techniques have improved the safety outcomes, there remains a need for additional improvement in those technologies that will enable better visibility of anatomy. Future device technologies are needed to provide improved imaging resolution and expanded 3-D imaging range and field of view.

Similarly, for procedures addressing structural heart defects, ICE provides important benefits, but also suffers from disadvantages that may hinder the achievement of ideal safety and performance outcomes. For example, the mono-planar nature of its images has been suggested to limit ICE's application to procedures such as the sizing of Left Atrial Appendage (LAA) occlusion devices⁽¹⁴⁾ and also other structural heart interventions generally⁽¹⁵⁾. Therefore, for the improvement of safety and performance outcomes in structural heart interventions, as with ablation procedures, it will be necessary to improve the resolution, far-field imaging and 3D capabilities of ICE.

The design of the VERAFEYE System, developed by LUMA Vision, employs a catheter concept providing 360° imaging and verification all around the catheter. The system enables high-resolution real-time anatomical imaging, while the catheter allows for dynamic navigation and requires minimal repositioning within the target anatomical structure. In combination with the dedicated processing in software, the VERAFEYE System can provide an advantage over commercially available ICE catheters by providing the operator with greater anatomical information.

**LUMINIZE_CLINICAL PROTOCOL**Document ID: VER-DOC-527
Controlled Document: VER-SIGN-3084TEMPLATE:
ONEPROJECTS/SIGN-267

Version: 4.0

Project: VERAFEYE (VER)
Date: 22-Nov-2024 14:16:10
Page: 12 / 51**5.3.1. RATIONALE FOR THE CLINICAL STUDY**

Numerous pre-clinical studies have demonstrated that the VERAFEYE System provides optimal visualization of anatomical structures that the Sponsor believes may lead to improved cardiac anatomical information and ultimately more effective treatment for patients undergoing electrophysiology and structural heart procedures. To further develop the VERAFEYE System, human data is required to assess the usability and integration of the VERAFEYE System in electrophysiology and structural heart workflows. Results from this study will be used to guide development and refinement the VERAFEYE System.

5.4. DEVICE DESCRIPTION**5.4.1. GENERAL**

The VERAFEYE System (Figure 1) comprises of a disposable VERAFEYE Imaging Catheter (VIC) and the VERAFEYE Imaging System. The Imaging System consists of a System Console (SC) and a Catheter Interface Unit (CIU). The individual devices listed in Table 1 must be used together and it is not allowed to combine with non-investigational devices.

**Figure 1: The VERAFEYE System**

The VERAFEYE Imaging System will be used according to the indications for use and the inclusion/exclusion criteria specified within this protocol. A copy of the device labeling and IFU will be provided in local language as required per national regulations.

**LUMINIZE_CLINICAL PROTOCOL**Document ID: VER-DOC-527
Controlled Document: VER-SIGN-3084TEMPLATE:
ONEPROJECTS/SIGN-267

Version: 4.0

Project: VERAFYE (VER)
Date: 22-Nov-2024 14:16:10
Page: 13 / 51

Table 1 provides an overview of the components of the VERAFEYE System, with their associated model numbers.

Table 1: VERAFEYE System

Individual Devices within the VERAFEYE System	Model Number
VERAFEYE Imaging Catheter	VF-VIC-001
VERAFEYE Imaging System	VF-VIS-001
System Console compromised of:	
System Console Computer	VF-SC-001
3D Tracking System	
Pulse Phase Module	
Catheter Interface Unit	VF-CIU-001

5.4.2. VERAFEYE IMAGING CATHETER

The VERAFEYE Imaging Catheter is a disposable, sterile, single-use component containing an ultrasound transducer at the tip. It is delivered by the VERAFEYE Imaging Catheter operator through femoral venous access to the patient's heart. It has bidirectional steering at the distal end through a handle to allow the user to navigate the cardiac structures. The transducer is rotating to allow a 360° view around the tip axis. The catheter tip contains a radiopaque element. The proximal end provides a connector that is plugged into the VERAFEYE Imaging System Catheter Interface Unit.

**LUMINIZE_CLINICAL PROTOCOL**Document ID: VER-DOC-527
Controlled Document: VER-SIGN-3084TEMPLATE:
ONEPROJECTS/SIGN-267

Version: 4.0

Project: VERAFEYE (VER)
Date: 22-Nov-2024 14:16:10
Page: 14 / 51**Figure 2: VERAFEYE Imaging Catheter****5.4.3. VERAFEYE IMAGING SYSTEM****5.4.3.1. System Console**

A non-sterile component for multiple use installed and used in the operational room of a hospital. The System Console is placed on a dedicated cart next to the patient bed. Consists of the following proprietary and off-the-shelf components:

- System Console Computer – the control and display unit of the VERAFEYE Imaging System which can be interacted with by the System Console operator via a keyboard and a computer mouse. It contains hardware to run the software of the VERAFEYE Imaging System (VeraApp). The software enables the hardware to control the Catheter Interface Unit, processes the data streams for visualization onto the display and provides the graphical user interface on the display to interact with the user. The System Console Computer operating hardware encompasses a central processing unit for running the operating system, graphics processing unit for processing the ultrasound data streams and displaying on the monitors. It also contains hardware for receiving Pulse Phase signals from the patient and hardware for tracking and location of the VERAFEYE Imaging Catheter tip through an electro-magnetic field.
- Monitors –components allowing for image display and manipulation to allow for image view and review for both VERAFEYE Imaging Catheter operator and System Console operator. The VERAFEYE Imaging System software on the Monitors is controlled by the users via an easy-to-

**LUMINIZE_CLINICAL PROTOCOL**Document ID: VER-DOC-527
Controlled Document: VER-SIGN-3084TEMPLATE:
ONEPROJECTS/SIGN-267

Version: 4.0

Project: VERAFYE (VER)
Date: 22-Nov-2024 14:16:10
Page: 15 / 51

use interface using multiple methods of input including a mouse, keyboard and/or a touch screen. Monitors interface with System Console Computer and displays the VERAFEYE Imaging System data acquisitions.

- 3D Tracking System – an electromagnetic tracking system to register the VERAFEYE Imaging Catheter's position in the heart. The non-sterile, multiple use system is comprised of an 3DTSensor Interface Unit that receives analogue tracking sensor signals from reference sensors on the patient's chest and back and from the VERAFEYE Imaging Catheter sensor inside the patient's heart. The unit transmits a digital signal to a 3DT-System Control Unit that receives signals from and provides power to the 3DT field generator. The System Console operator connects the reference sensors and places the EM Field Generator close to the patient's chest to capture the sensor positions. The tracking signal will not be displayed to the VERAFEYE Imaging Catheter operator during the procedure but will be registered in the background. The System Console operator can tune the signal in the tracking's setup window in the GUI.
- Pulse Phase Module – a module that receives and transmits heartbeat signals to the System Console Computer. The Pulse Phase signal will not be displayed to the VERAFEYE Imaging Catheter operator during the procedure but will be registered in the background. The System Console operator can tune the signal in a setup window in the GUI.

[figure not shown]
5.4.3.2. Catheter Interface Unit

A non-sterile component for multiple use intended to send and receive analog signals to/from the VERAFEYE Imaging Catheter. The sterile, single-use VERAFEYE Imaging Catheter is plugged into the non-sterile Catheter Interface Unit. The Catheter Interface Unit receives signals from the VERAFEYE Imaging Catheter, converts them into digital signals and transports them through optical fibers to the System Console Computer. Furthermore, the Catheter Interface Unit contains a motor drive for rotating the transducer in the VERAFEYE Imaging Catheter. The motor and the ultrasound conversion unit are controlled by the System Console Computer. The conversion unit rotates, the power, control and data signals are transmitted through rotating joints. The Catheter Interface Unit is placed on a dedicated cart next to the patient's bed and with proximity to the System Console cart.

Figure 3 provides an example of the room setup during a procedure.

**LUMINIZE_CLINICAL PROTOCOL**Document ID: VER-DOC-527
Controlled Document: VER-SIGN-3084TEMPLATE:
ONEPROJECTS/SIGN-267

Version: 4.0

Project: VERAFEYE (VER)
Date: 22-Nov-2024 14:16:10
Page: 16 / 51**Figure 3: Room Setup During Procedure****5.4.4. INDICATIONS FOR USE/CONTRAINDICATIONS**

The VERAFEYE System is intended to be used for real-time, minimally-invasive guidance of endovascular and intracardiac procedures, e.g. such as cardiac ablation, structural heart procedures, or transseptal punctures. The system provides image information of cardiovascular anatomic features, physiological information of cardiovascular structures and features, and spatial relationships of other devices within the heart and great vessels. Please refer to the IFUs for an overview of contraindications.

5.5. STUDY OBJECTIVE

The objective of the study is to collect data on the usability and integration of the VERAFEYE System in standard of care

- catheter-based ablation treatments for Typical Atrial Flutter (AFL) or Atrial Fibrillation (AF)
- left atrial appendage closure (LAAC) procedures
- atrial septal defect (ASD) closure procedures

Results from this study will be used to guide development and refinement the VERAFEYE System.

**LUMINIZE_CLINICAL PROTOCOL**Document ID: VER-DOC-527
Controlled Document: VER-SIGN-3084TEMPLATE:
ONEPROJECTS/SIGN-267

Version: 4.0

Project: VERAFEYE (VER)
Date: 22-Nov-2024 14:16:10
Page: 17 / 51**5.6. STUDY ENDPOINTS**

This is a feasibility study and no formal endpoints or hypothesis testing are planned in the study. The study is not designed to collect data for product approval and as such does not have a safety or efficacy endpoint.

5.7. STUDY DESIGN

This is a prospective, non-randomized, single-arm feasibility study. This study is a pilot stage study according to ISO/FDIS 14155: 2020 (E) - Annex I. Results from this study will be used to guide development and refinement of the VERAFEYE System.

The study is designed to assess the usability and integration of the VERAFEYE System in standard of care, catheter-based ablation treatments for Typical Atrial Flutter (AFL) or Atrial Fibrillation (AF), standard of care left atrial appendage closure (LAAC) procedures and standard of care atrial septal defect (ASD) closure procedures. Results from this study will be used to guide development and refinement the VERAFEYE System.

Intended Users of the VERAFEYE System are interventional cardiologists and electrophysiologists who are trained in percutaneous and transseptal procedures and who have completed the VERAFEYE System training. The VERAFEYE System training is offered by the Sponsor. The VERAFEYE System should only be performed by these Intended Users.

A prospective study design will ensure that identical procedures are followed for data capture and review.

Up to 4 operators per site will be allowed to perform study procedures, unless written approval from LUMA Vision was obtained.

A sample size of 40 subjects was chosen to allow for sufficient feasibility testing and data collection for the ablation, LAA and ASD closure procedures. The sample size is not statistically based but is based on a reasonable number of data sets to assess the images collected with the VERAFEYE System.

In protocol rev 4.0, the sample size was extended from 20 subjects to 40 subjects, in order to collect more clinical data for further system development and to ensure the collection of information from different operators.

Enrolment in this study is competitive, there is no limit of enrolments per site.

Subject procedures will follow a sequential pattern (one site after the other) to allow LUMA Vision field support personnel to be present during the procedures and to ensure the availability and installation of necessary equipment.

[figure not shown]
Enrolment in the study is expected to be completed in approximately 6 months. The follow-up for each participant is expected to be approximately 7 days, therefore the total study duration is expected to last approximately 7 months.

**LUMINIZE_CLINICAL PROTOCOL**Document ID: VER-DOC-527
Controlled Document: VER-SIGN-3084TEMPLATE:
ONEPROJECTS/SIGN-267

Version: 4.0

Project: VERAFFEYE (VER)
Date: 22-Nov-2024 14:16:10
Page: 18 / 51

The Figure below shows the schematic of the study design.

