**LUMINIZE_CLINICAL PROTOCOL**

Document ID: VER-DOC-527
Controlled Document: VER-SIGN-3084

Study enrolment will be considered as complete when 40 procedure subjects have been enrolled (see section 'subject classification').

Enrolment in the study is expected to be completed in approximately 6 months. The follow-up for each participant is expected to be approximately 7 days, therefore the total study duration is expected to last approximately 7 months.

Up to 2 sites in Ireland may participate in the study. Enrolment in this study is competitive, there is no limit of enrolments per site.

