5.9.2. SUBJECT CLASSIFICATION

- Enrolled subject- Any participant who signs the informed consent form.
- Screen Failure subject- Any participant who signs the consent form but is found to not meet eligibility criteria.
- Intent subject- Any participant who signs the consent form, met the eligibility criteria but did not have the VERAFEYE Imaging Catheter inserted into the body.
- Attempt subject- Any participant who signs the consent form, met the eligibility criteria, did have the VERAFEYE Imaging Catheter inserted into the body but did not undergo the ablation/LAA/ASD closure procedure per this study protocol.
- Procedure subject - Any participant who undergoes the ablation/LAA/ASD closure procedure with the VERAFEYE System as imaging system per this study protocol.

These subjects are followed in accordance with the Follow-Up schedule and data will be included in all study analyses.

[figure not shown]
- Withdrawn subject - A participant who chooses to or is withdrawn from the study.
- Lost-to-follow up subject - A participant who cannot be reached anymore after 3 attempts.

Enrolment will be considered as complete when 20 procedure subjects have been enrolled.

The Figure below shows the subject classifications.

**LUMINIZE_CLINICAL PROTOCOL**Document ID: VER-DOC-527
Controlled Document: VER-SIGN-3084TEMPLATE:
ONEPROJECTS/SIGN-267

Version: 4.0

Project: VERAFYE (VER)
Date: 22-Nov-2024 14:16:10
Page: 22 / 51**Figure 5: Subject Classifications****5.9.3. END OF STUDY**

Individual study subject participation will end when the last subject follow-up visit is completed; when the subject withdrew or was withdrawn from the study or when the subject is considered as lost-to-follow up.

The study will be considered as complete when the last subject's follow up visit occurs or when subjects are no longer being considered for participation. Routine management and standard practice of care will continue for the subjects who have completed the study.

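### Section 5.9.2 closes enrolment at 20 procedure subjects, while the synopsis, 5.7 and 5.9.1 all set 40

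*Combined protocol and SAP*

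**What the plan says.** Four places in the current protocol bear on when enrolment ends.

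- Section 5.2 (synopsis): "Enrolment will be considered as complete when 40 subjects have completed the ablation, or LAA/ASD closure procedure", with the VERAFEYE System as imaging system.
- Section 5.7: the sample size is 40. In protocol revision 4.0 "the sample size was extended from 20 subjects to 40 subjects", and the reason given is "in order to collect more clinical data for further system development and to ensure the collection of information from different operators".
- Section 5.9.1: "Study enrolment will be considered as complete when 40 procedure subjects have been enrolled". This sentence carries a cross-reference to the subject classification section.
- Section 5.9.2, the subject classification section: "Enrolment will be considered as complete when 20 procedure subjects have been enrolled".

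Section 5.12 adds that the study data will be summarised in a clinical study report when enrolment concludes.

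On operators, 5.7 says "Up to 4 operators per site will be allowed to perform study procedures, unless written approval from LUMA Vision was obtained", and 5.10.3.1 repeats this. The synopsis and 5.9.1 allow up to 2 sites. Section 5.7 also says "Enrolment in this study is competitive, there is no limit of enrolments per site".

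**The concern.** The rule that ends enrolment should have one value. Here, three sections give or imply 40 and one gives 20, which is the number that 5.7 says was replaced. The odd one out is also the section that defines a procedure subject, the unit being counted, and 5.9.1 points to it.

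A site or monitor working from 5.9.2 would have a textual basis for treating enrolment as complete at 20, or for querying cases 21 to 40. At stake are the 20 additional data sets that the revision was written to obtain and the timing of the report under 5.12. The timing problem is a consequence of the same number and not a second error.

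**Working it through.** There is no sample-size calculation to reproduce. Section 5.7 says the number is not statistically based, and it gives no power, error rate or effect size. The check is therefore a comparison of the current sections.

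| Section | Unit counted | Number |
|---|---|---|
| 5.2 Synopsis | subjects who completed the procedure with the study system | 40 |
| 5.7 Study Design | subjects (planned sample size) | 40, extended from 20 |
| 5.9.1 Point of Enrolment | procedure subjects | 40 |
| 5.9.2 Subject Classification | procedure subjects | 20 |

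**Could both numbers be right because they count different things?** No. Sections 5.9.1 and 5.9.2 use the same unit, the procedure subject. Section 5.9.2 defines this as a participant who undergoes the procedure with the study system as imaging system, and the synopsis describes the same people.

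**Is this only a difference from the version history?** No. All four statements stand in the body of version 4.0. The version history lists 5.9.2 among the sections updated to 40. That suggests which number was meant, but the conflict does not depend on it.

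**Size of the gap.** 40 − 20 = 20 procedure subjects, and 20/40 = 50% of the planned number. The extension itself was 40 − 20 = 20 cases, so a close at 20 would forgo all of it.

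**Does the operator aim depend on the count?** The readable ceilings, without written sponsor approval, are 1 site × 4 = 4 operators or 2 sites × 4 = 8 operators. Mean cases per operator at those ceilings:

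| Operators | At 20 cases | At 40 cases |
|---|---|---|
| 4 (one site) | 20/4 = 5 | 40/4 = 10 |
| 8 (two sites) | 20/8 = 2.5 | 40/8 = 5 |

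Several operators can contribute under either count. Equally, no readable rule would be broken if one operator performed all the cases. The count settles how many data sets are collected. It does not by itself settle how many operators supply them.

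**After correction.** With 40 in 5.9.2, all four sections agree.

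**The case against.** The best defence is that nobody would be misled. Section 5.7 states outright that 20 became 40, and the synopsis and 5.9.1 agree with it. The cross-reference in 5.9.1 is presumably there for the definition of a procedure subject. A sponsor representative attends every procedure (5.10.3.2), so a site is unlikely to stop at 20 unnoticed. Most of this stands, and it lowers the practical risk. It does not remove the sentence in 5.9.2, which is current text and gives a different closing number.

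Two stronger readings are tempting, and the documents support neither.

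- *A reader might infer that the operator aim in 5.7 is defective because no minimum number of operators is written.* The sentence in 5.7 explains why the sample was enlarged; it is not an operating rule. The sponsor authorises the operators (5.10.3.1) and attends each case, so it can influence the mix. Section 5.10.3.4 also provides for a physician questionnaire rating the system. By the arithmetic above, two or more operators can be reached at 20 or at 40. What remains is wording: ensuring is a stronger promise than a set of maximums can deliver.
- *A reader might infer that the report must tabulate cases by operator.* Section 5.12 promises descriptive statistics only. The data list in 5.10.3.4 has no operator item, and Table 9 keeps the signed Technical Source Form at the site. Such a table would be an addition to the plan, possibly with a new data item, and its absence is not an error.

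**Conclusion.** The point holds as an internal contradiction in the enrolment-completion rule. Section 5.9.2 says 20, while 5.2, 5.7 and 5.9.1 say 40. The difference is 20 procedure subjects, half the planned study, and the date of the report moves with it.

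That 40 is the intended number is an inference, but a strong one: three sections agree, and 5.7 explains the change. Figures 4 and 5 are not visible in the copy reviewed. A figure could show a count or an allocation, but it could not cancel the sentence in 5.9.2.

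A reader might go further and infer a loss of power or a compromised test. The documents do not support that. Section 5.6 plans no formal endpoint or hypothesis test, and 5.7 says the sample size is not statistically based. The consequence is confined to when enrolment ends, how many data sets are collected and when they are reported. The operator wording in 5.7 is a matter of preference and does not add to the size of the finding.

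**What to change.** Change 20 to 40 in the completion sentence of 5.9.2, so that one count governs the end of enrolment and the timing of the report in 5.12. Check Figures 4 and 5 for a remaining 20 at the same time.

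The cost is one number, in an amendment that needs ethics committee approval and regulatory authority approval as applicable (5.14.9). No subjects beyond the 40 already planned are needed, and no analysis changes.

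Optionally, the same amendment could reword 5.7 so that information from different operators is an aim of the extension and not something it ensures. That is one phrase. It gives up a promise that the readable rules do not secure, and it adds no operational burden.
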